#### 6.2.7. Treatment Satisfaction Questionnaire for Medicine

Scores for each domain are computed by adding the TSQM items in each domain and then transforming the composite score into a value ranging from 0 to 100. Of note, a score can be computed for a domain only if no more than 1 item is missing from that domain. The calculations specific to each domain are presented in detail below.

**Table 21: Algorithms for TSQM-9 Domain Score Calculation**

Domain	Item Missingness	Formula
Effectiveness (Items 1 to 3)	If items 1, 2, and 3 are nonmissing	$100 \times \frac{[\text{Sum}(\text{Item 1 to Item 3}) - 3]}{18}$
	If 1 item is missing	$100 \times \frac{[\text{Sum}(\text{the two completed items}) - 2]}{12}$
Convenience (Items 4 to 6)	If items 4, 5, and 6 are nonmissing	$100 \times \frac{[\text{Sum}(\text{Item 4 to Item 6}) - 3]}{18}$

**Table 21: Algorithms for TSQM-9 Domain Score Calculation**

Domain	Item Missingness	Formula
	If 1 item is missing	$100 \times \frac{[\text{Sum}(\text{the two completed items}) - 2]}{12}$
Global Satisfaction (Items 7 to 9)	If items 7, 8, and 9 are nonmissing	$100 \times \frac{[\text{Sum}(\text{Item 7 to Item 9}) - 3]}{14}$
	If either Item 7 or Item 8 is missing	$100 \times \frac{[\text{Sum}(\text{the two completed items}) - 2]}{10}$
	If Item 9 is missing	$100 \times \frac{[\text{Sum}(\text{item 7 and item 8}) - 2]}{8}$

Abbreviation: TSQM-9 = Treatment Satisfaction Questionnaire for Medication

**6.2.8. European Quality of Life Health 5-item Questionnaire Health State Index Calculations**

The responses to the 5 EQ-5D-5L dimensions can be converted into a single number called an index value. The index value can be calculated by subtracting the appropriate weights listed in [Table 22](#) for each dimension level of health state from 1. The weight for this study is provided by the US composite time trade-off (cTTO) method. The calculation is illustrated in [Table 22](#).

**Table 22: EQ-5D-5L US Composite Time Trade-off Value Set**

US TTO		Example: the value for health state 21354
Full health (11111)		Full health = 1
Mobility		
Mobility level 2	-0.096	-0.096
Mobility level 3	-0.122	
Mobility level 4	-0.237	
Mobility level 5	-0.322	
Self-care		
Self-care level 2	-0.089	0
Self-care level 3	-0.107	
Self-care level 4	-0.220	
Self-care level 5	-0.261	
Usual activity		
Usual activity level 2	-0.068	
Usual activity level 3	-0.101	-0.101
Usual activity level 4	-0.255	
Usual activity level 5	-0.255	
Pain/discomfort		
Pain/discomfort level 2	-0.06	
Pain/discomfort level 3	-0.098	
Pain/discomfort level 4	-0.318	
Pain/discomfort level 5	-0.414	-0.414
Anxiety/depression		
Anxiety/depression level 2	-0.057	
Anxiety/depression level 3	-0.123	
Anxiety/depression level 4	-0.299	-0.299
Anxiety/depression level 5	-0.321	

**Table 22: EQ-5D-5L US Composite Time Trade-off Value Set**

US TTO		Example: the value for health state 21354
Health State Index Score		= 1 - 0.096 + 0-0.101 - 0.414 - 0.299 = 0.090

Abbreviations: EQ-5D-5L = European Quality of Life Health 5-item questionnaire; TTO = time trade-off; US = United States

**6.2.9. Analysis Windows**

Since the actual study visits for a participant may not exactly coincide with their targeted visit date, the actual visit date will be mapped to the analysis visits as described below.

The analysis visits for the RCP will be derived using prespecified windows around the number of days during the study since the first dose of the study drug (called Day 1). The lower and the upper limits of the analysis windows are described in [Table 23](#).

**Table 23: Analysis Windows for Randomized Controlled Period**

Analysis Visit	Target Day	Low	High
Week 2	15	2	29
Week 6	43	30	57
Week 10	71	58	85
Week 14	99	86	113
Week 18	127	114	141
Week 22	155	142	169
Week 26	183	170	211
Week 34	239	212	267
Week 42	295	268	323
Week 50	351	324	For participants entering OLE, the day of first dose in OLE; the last day in the study for other participants

The analysis visits for the OLE Period will be derived using prespecified windows around the number of days during the study since the first dose of the OLE Period. The lower and the upper limits of the analysis windows are described in [Table 24](#).

**Table 24: Analysis Windows for Open-Label Extension Period**

Analysis Visit	Target Day	Low	High
Week 2	15	2	43
Week 10	71	44	99
Week 18	127	100	155
Week 26	183	156	211
Week 34	239	212	267
Week 42	295	268	323
Week 50	351	324	379
Week 58	407	380	435
Week 66	463	436	491
Week 74	519	492	547

**Table 24: Analysis Windows for Open-Label Extension Period**

Analysis Visit	Target Day	Low	High
Week 82	575	548	603
Week 90	631	604	659
Week 98	687	660	715
Week 106	743	716	-

**6.2.9.1. Rules for Selecting the Analysis Records**

Only 1 record per analysis window will be selected for analysis. The following defines the selection rule.

1. Only scheduled visits of the specific endpoint will be selected and summarized in the tables and figures. If the earlier versions of the protocol and the final version of the protocol have different assessment schedules, then both scheduled visits will be used for the descriptive summary, as appropriate. Only the scheduled visits in the latest protocol will be selected for inferential analysis.
  - a. For example, an unscheduled SVC assessment may fall into the Week 22 analysis window. However, because Week 22 is not a scheduled visit for SVC, this record will not be flagged for descriptive and inferential analysis.
2. If there are multiple non-missing records within the same analysis window, the record closest to the target day will be selected.
3. If there are records with equal distance from the target day, the later record will be selected.
4. For CAFS analysis, only the last nonmissing record of ALSFRS-R will be selected.

Similar visit windows will be implemented for the OLE Period.

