**Table 1: Schedule of Activities: Screening to Week 50**

Period	Screening	Randomized Controlled Period												Notes
Visit a	1	2	3	4	5	6	7	8	9	10	11	12 b	13	Additional visits can be performed as needed. An ED Visit should be performed if patients discontinue early.
Week	Up to 4 W		W2	W6	W10	W14	W18	W22	W26	W34	W42	W46	W50/ ED in RCP c	
Days and Window		D1	D15 ± 2	D43 ± 3	D71 ± 3	D99 ± 3	D127 ± 3	D155 ± 3	D183 ± 3	D239 ± 3	D295 ± 3	D323 ± 3	D351 ± 3	
C-SSRS e		B			X		X		X	X	X		X	C-SSRS Screening/baseline version (B) to be performed at Day 1 and Since Last Visit version (X) at all other timepoints.
Pharmacokinetic and Pharmacodynamic Assessments														
Blood samples for PK/free C5		B/P	T/P		T/P		T/P		T/P	T/P	T/P		T	At ED visit, samples can be anytime.
Blood samples for ADA		B			T				T				T	At ED visit, samples can be anytime.
Biomarker Research														
Blood samples for biomarker		B	T		T				T	T			T	At ED visit, samples can be anytime.
Blood samples for DNA and RNA		B	T						T					Optional; collect samples from patients who consent to DNA and RNA collection. The blood sample for RNA is collected at all time points and the blood sample for DNA is collected on Day 1. i
Urine samples for biomarkers		X	X						X				X	

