### **8.3.9. Suicidal Ideation and Behavior Risk Evaluation**

Patients being treated with a study drug for a neurologic indication should be evaluated prospectively for suicidal ideation or behavior during the study.

In this study, the Columbia-suicide severity rating scale (C-SSRS) will be used to monitor suicidal ideation and behavior. The Baseline/Screening version (Section 10.11) will assess lifetime risk as well as risk in the past 12 months. Intervention-emergent suicidal ideation and behavior will be monitored using the C-SSRS-Since Last Visit version (Section 10.12).

The C-SSRS will be performed by the Investigator or an appropriately trained designee at visits specified in the SoA (Section 1.3) to ensure that patients who are experiencing suicidal thoughts or behavior are properly recognized and adequately managed or referred for further evaluation. Additional C-SSRS assessments are permitted as needed.

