**Table 14: Composite Endpoints Based on C-SSRS**

Endpoint	Description
Suicidal ideation	A “yes” answer to any of the 5 suicidal ideation questions (Categories 1-5) on the C-SSRS.
Suicidal behavior	A “yes” answer to any of the 5 suicidal behavior questions (Categories 6-10) on the C-SSRS.
Suicidal ideation or behavior	A “yes” answer to any 1 of the 10 suicidal ideation and behavior questions (Categories 1-10) on the C-SSRS.

The following analyses will be performed:

- The number and percentage of participants who experience an event at Baseline (“Lifetime” and “past 12 months,” separately) and at least once during the treatment period will be summarized by the treatment group for
  - Each of the 3 composite endpoints in [Table 14](#)
  - The self-injurious behavior without suicidal intent
- A shift tabulation from Baseline (“Lifetime” and “past 12 months,” separately) will be produced by treatment group during the RCP against the 3 composite endpoints for each of the 3 following groupings:
  - No suicidal ideation or behavior,
  - Composite endpoint of suicidal ideation, and
  - Composite endpoint of suicidal behavior. Each participant is counted once in 1 cell only for each of the 2 tabulations. Participants with both suicidal ideation and suicidal behavior are included in the suicidal behavior category for the shift analysis.

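### Read literally, SAP 6.2.9.1 keeps unscheduled and some early-discontinuation C-SSRS forms out of the any-time counts and shift table planned in SAP 5.6.8

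*SAP*

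**What the plan says.** The record rules are in SAP 6.2.9.1, which opens with: "Only 1 record per analysis window will be selected for analysis". Rule 1 reads: "Only scheduled visits of the specific endpoint will be selected and summarized in the tables and figures". Its example is an unscheduled SVC assessment in the Week 22 window, a week without a planned SVC, and it concludes that "this record will not be flagged for descriptive and inferential analysis". Rule 2 reads: "If there are multiple non-missing records within the same analysis window, the record closest to the target day will be selected". Rule 3 breaks ties in favor of the later record. Rule 4, for CAFS, is the only one tied to an endpoint.

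SAP 5.6.8 reports the number and percentage of participants with an event at baseline and "at least once during the treatment period will be summarized by the treatment group". This covers the three composites of Table 14 and self-injury without suicidal intent. The same section plans a shift table from baseline for the RCP. It does not say which post-baseline records feed either output.

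On collection, Protocol 8.3.9 says: "Additional C-SSRS assessments are permitted as needed". The C-SSRS row of Protocol Table 1 says: "C-SSRS Screening/baseline version (B) to be performed at Day 1 and Since Last Visit version (X) at all other timepoints". After Day 1 the form is scheduled at Weeks 10, 18, 26, 34 and 42 and in the shared Week 50/ED column. It is not scheduled at Weeks 2, 6, 14 or 22.

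**The concern.** Picking one record per window suits a measure of current state, such as ALSFRS-R or SVC, where a neighboring value is a fair substitute. It does not suit a form that asks about an interval. Each Since Last Visit form covers its own stretch of time, so dropping one leaves that stretch uncovered.

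The forms most exposed are an extra C-SSRS done outside the schedule, possibly because someone was worried, and the last form before a participant leaves the trial. Losing them can only lower the count of participants with suicidal ideation or behavior. With the trial stopped for futility and its p-values declared descriptive, the safety tables are among the outputs that will still be used.

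**Working it through.** The plan states no figure to reproduce. The check applies the rules to the windows.

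**Inputs.** RCP windows from SAP Table 23: Week 2 (Days 2-29), Week 6 (30-57), Week 10 (58-85), Week 14 (86-113), Week 18 (114-141), Week 22 (142-169), Week 26 (170-211), Week 34 (212-267), Week 42 (268-323), Week 50 (from 324). Target days: 71, 127, 183, 239, 295 and 351 for the C-SSRS weeks. Assumption: scheduled forms are completed on the target day.

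**Case 1, unscheduled form.** The Week 10 form on Day 71 is negative. An extra form on Day 100 is positive. The Week 18 form on Day 127 asks about the time since the last visit, here taken as Day 100, and is negative. Day 100 lies in the Week 14 window, which has no scheduled C-SSRS, so rule 1 excludes it. The participant is shown as having no ideation or behavior.

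Moving the extra form into a C-SSRS window does not help. On Day 78 it would sit in the Week 10 window. Rule 1 still excludes it as unscheduled, and rule 2 would exclude it as well, since 78 - 71 = 7 days from target against 0.

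**Case 2, ED form sharing a window.** A scheduled form on Day 183 is negative and an ED form on Day 205 is positive. Both fall in the Week 26 window. The distances from target are 0 and 205 - 183 = 22 days. Rule 2 keeps Day 183, and the interval from Day 183 to Day 205 is not counted. This happens even if ED counts as a scheduled visit.

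**Where an ED form can fall.** Days 2 to 350 are 349 days:
- In Week 2, 6, 14 or 22 windows: 4 x 28 = 112 days (32%). The rules do not say whether an ED form here counts as scheduled.
- After the target day in a C-SSRS window: 14 + 14 + 28 + 28 + 28 = 112 days (32%). Rule 2 drops the ED form.
- Before the target day in a C-SSRS window: 13 + 13 + 13 + 27 + 27 + 27 = 120 days (34%). The ED form has no competitor and is kept.
- On a target day: 5 days.

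Check: 112 + 112 + 120 + 5 = 349. These are shares of calendar days, not of participants.

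**Comparison with other safety sections.** SAP 5.6.3, 5.6.4 and 5.6.5 give labs, vital signs and ECG their own rule, the last record. SAP Table 7 includes any post-baseline value for ALT and AST, and SAP Table 11 uses the maximum post-baseline QT. SAP 5.6.8 has nothing equivalent, so whoever programs the C-SSRS tables has only 6.2.9.1 to follow.

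**The case against.** The best reply is that 6.2.9.1 was never meant for these tables. Section 6.2.9 maps visit dates to analysis visits. The ALSFRS-R model section cross-refers to it and 5.6.8 does not. The C-SSRS counts are not by visit, and an any-time count can naturally be read as using every record. Several safety sections already depart from rule 2. This reply stands in part: the defect is a conflict between two sections, not a proven loss. But rule 1 is worded generally, its example reaches descriptive summaries, and nothing in 5.6.8 overrides it.

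The stakes are also limited. C-SSRS shift is an exploratory endpoint, the safety analyses are descriptive, both arms are affected, and rule 1 governs tables and figures, not listings. All of that is fair. It lowers the priority but does not repair the tables.

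Two stronger readings are tempting and not supported.

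- A reader might infer that every completed suicide drops out. No passage says when the form is completed after a death. The Since Last Visit form has a Suicide item, and Protocol Table 1 marks C-SSRS at the Week 50/ED visit. If the event is recorded on an ED form, the form would be selectable on 120 of 349 days (34%), or on 120 + 112 = 232 of 349 (66%) if off-schedule windows are allowed. It is lost from the composite only if it is recorded solely on a form that is not selected. Deaths by reason (SAP 5.4.1.1.3) and adverse events leading to death (SAP Table 6) do not pass through these rules.
- A reader might turn the day counts into participants: 224/349 = 64% of ED forms, times 20% dropout, times 354, giving about 45. That assumes evenly spread ED dates, an ED form from every dropout (Protocol 7.2 asks for the visit only where possible), and that off-schedule windows bar ED forms. It also applies planning values to a trial that stopped early. Above all, it counts forms not selected, not missed suicidality.

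**Conclusion.** The point holds as a conflict between sections. Following 6.2.9.1 as written removes unscheduled C-SSRS forms, and ED forms that share a window with a scheduled form nearer the target day, from the at-least-once counts and the RCP shift table.

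A participant is misclassified only if no selected form is positive; continuing or repeated ideation on a selected form is still counted. The direction is certain (undercount), but the number of participants cannot be derived from the documents.

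The conclusion rests on reading rules 1 and 2 as general and on each form covering only the time since the preceding assessment. If the sponsor intended all records to count, the text needs to say so. It should be settled before the C-SSRS tables are produced.

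**What to change.** Add to SAP 5.6.8, with a cross-reference in 6.2.9.1:

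*The at-least-once summaries and the shift tables use all post-baseline C-SSRS records in the RCP before the first OLE dose, whether scheduled, unscheduled, from an ED visit, or completed after a death. Each participant is classified by the most severe category reported. Rules 1 to 3 of Section 6.2.9.1 do not apply to these tables.*

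Keep the Table 14 definitions as they are, based on answers on the C-SSRS. Counting suicides from the death record would change the endpoint, and deaths are already tabulated elsewhere.

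The cost is a short SAP insertion and a programming step that takes the worst of all records. It needs no new data and no protocol amendment.

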**6.3. Appendix 3: List of Abbreviations**

The following abbreviations are used in this SAP.

**Table 25: Abbreviations**

Abbreviation	Definition
ADA	Antidrug antibody
AE	Adverse event
ALP	Alkaline phosphatase
ALS	Amyotrophic lateral sclerosis
ALSAQ-40	ALS assessment questionnaire
ALSFRS-R	Amyotrophic lateral sclerosis functional rating scale revised
ALT	Alanine aminotransferase
ANCOVA	Analysis of Covariance
AST	Aspartate aminotransferase
ATC	Anatomical therapeutic chemical
BMI	Body mass index
CAFS	Combined assessment of function and survival
C-SSRS	Columbia-Suicide Severity Rating Scale
CV	Coefficient of variation

**Table 25: Abbreviations**

Abbreviation	Definition
ECG	Electrocardiogram
ED	Early discontinuation
EQ-5D-5L	European Quality of Life Health 5-item questionnaire
FAS	Full Analysis Set
FDA	Food and Drug Administration
HHD	Handheld dynamometry
HR	Hazard ratio
IAP	Interim analysis plan
ICE	Intercurrent Event
IDMC	Independent data monitoring committee
IP	Investigational product
IV	Intravenous
KSS	King's staging system
LS	Least squares
MAR	Missing at random
MCS	Mental component summary
MedDRA	Medical Dictionary for Regulatory Activities
MMRM	Mixed-effects model repeated measures
NfL	Neurofilament
NIV	Noninvasive ventilation
OLE	Open-Label Extension
OLES	Open-Label Extension Set
PAV	Permanent assisted ventilation
PCS	Physical component summary
PD	Pharmacodynamics
PDAS	Pharmacodynamic Analysis Set
PK	Pharmacokinetics
PKAS	Pharmacokinetic Analysis Set
PRO-ACT	Pooled Resource Open-Access ALS Clinical Trials
PT	Preferred term
PTAEs	Pre-Treatment Adverse Events
RCP	Randomized-controlled period
SAP	Statistical analysis plan
SD	Standard deviation
SF-36	Short-Form Health Survey
SoA	Schedule of activities
SOC	System organ class
SS	Safety Set
SVC	Slow vital capacity
TBL	Total bilirubin
TEAE	Treatment-emergent adverse event
TSQM-9	Treatment Satisfaction Questionnaire for Medication
ULN	Upper limit of normal
VAFS	Ventilation assistance-free survival
VAS	Visual analog scale
WHO	World health organization

## 6.4. Appendix 4: Changes to Protocol-planned Analyses

The following table summarizes the changes in the planned analyses compared to the SAP version 1.0.

Section # and Name	Description of Changes	Brief Rationale
1.INTRODUCTION	
The following texts have been deleted:
 
The scope of this analysis plan includes all efficacy, safety, pharmacokinetics, pharmacodynamics, and immunogenicity data collected during the randomized-controlled period. It will also include select analyses for the open-label extension period data available at the time of database lock for submission to the regulatory agencies. A separate analysis plan will be created to describe the planned analysis methods for the open-label extension period before the final database lock (study closeout).
 
The table, figure, and listing specifications will be provided in a separate Data Presentation Plan document.
 
The following texts have been added:
 
The scope of the analyses for this study has been revised and is reflected in this SAP amendment due to the study meeting the pre-specified futility criterion. The amendment will be finalized prior to the final database lock and randomization code release. No separate SAP will be developed for the open-label extension period of the study.
	Describe the reason for the SAP amendment and some corresponding plan.
4.ANALYSIS Table 25: Analysis Sets	Per-Protocol Set (PPS) and Ravulizumab Exposure Set (RTS) have been deleted from Table 2.	
The PPS analyses are not meaningful as the study stopped due to futility.
 
Given a small amount of data for the open-label extension period, the analyses based on RTS will be redundant.

5.1 General Consideration	
The following texts have been added:
 
All p-values and confidence intervals will be used for descriptive purposes only due to the study meeting the futility criterion.
	To explain how the p-values and confidence intervals will be interpreted.
5.2 Study Participants	Deleted the randomized by region information	Reduced scope for the abbreviated CSR.
5.3.3 Alternate Primary Estimand and Analysis	Deleted this section	Not meaningful given the futility decision.
5.3.4 Other Analyses	Deleted the ALSFRS-R subscore summaries.	Reduced scope for the abbreviated CSR.
5.3.4.2 -5.3.4.8 Sensitivity Analysis 2-8	Deleted	Not meaningful given the futility decision.
5.3.5 Supplementary Analyses	Deleted	Not meaningful given the futility decision.

5.3.6 Other Analyses	Deleted the following sentence:  In addition, longitudinal changes in ALSFRS-R subscores will be modeled using the analytical approach described in Section 5.3.4.1	Not meaningful given the futility decision.
5.4.1.1.3 Sensitivity Analysis of VAFS	Deleted	Not meaningful given the futility decision.
5.4.1.1.4 Other Analyses Related to VAFS and Components of VAFS (NIV, PAV and Mortality)	Deleted the following sentences: The log-rank tests will also be performed for these endpoints. The Vonesh Shared Parameter model described in Section 5.3.4.3 will be used for joint estimation of treatment effect on mortality and ALSFRS-R.	Not meaningful given the futility decision.
5.4.1.3 Sensitivity Analysis: Slow Vital Capacity Percent Predicted	Deleted	Not meaningful given the futility decision.
5.4.1.4 Other Analyses for Slow Vital Capacity	Deleted the following: An analysis of the change from baseline in slow vital capacity volume (Liter) will be conducted similar to the method described in Section 5.4.1.2.2.	Not meaningful given the futility decision.
5.4.2 Supportive Secondary Endpoints and Analysis	Deleted the MMRM analyses for HHD and NfL.	Not meaningful given the futility decision.
5.5 Tertiary/Exploratory Endpoints and Analyses	Deleted all the analyses for tertiary/exploratory endpoints	Reduced scope for the abbreviated CSR.
5.6 Safety Analyses	Deleted all analyses related to Ravulizumab Exposure Set.  Deleted all summary analyses for OLE except the first 6 TEAE tables in Table 6.  For RCP, added the following in Table 6: -TEAEs (IP related) by SOC and PT; -TESAEs by SOC and PT and by Highest Relationship to IP; Changed the following in Table 6: -TESAEs (IP related) by SOC, PT and by Highest Severity to -TESAEs (IP related) by SOC and PT  Added the following listings and tables: Listings: -Infusion reaction related AEs -COVID-19 AEs  Tables: - Infusion reaction related AEs by SOC and PT - Infusion reaction related SAEs by SOC and PT - Infusion reaction related AEs (IP-related) by SOC and PT - Overall Summary of COVID-19 related AEs - COVID-19 related AEs by SOC and PT - COVID-19 related SAEs by SOC and PT	Given a small amount of data for the open-label extension period, the analyses based on RTS or OLES will be redundant or not meaningful.  Additional output to support safety evaluation of ravulizumab.

5.6.1 Extent of Exposure	Deleted the worst post baseline value analyses	
5.6.3 Laboratory Tests	Deleted the following variables from Table 4: Ravulizumab Treatment Duration(days) Total Patient-years (years) Ravulizumab exposure Total number of ravulizumab infusions	RTS was dropped.
5.6.6 Physical Examination	Deleted the following:  The number and percentage of participants with normal and abnormal findings for each physical examination category will be reported by visit for the RCP and the OLE. Participants reporting 'not done' will not be included in the denominator for the percentage calculation.	Reduced scope for the abbreviated CSR.
5.6.7 Neurological Examination	Deleted the following:  The number and percentage of participants with different findings for each neurological examination category will be reported by visit for the RCP and the OLE.	Not meaningful given the futility decision.  Reduced scope for the abbreviated CSR.
5.6.9 COVID-19 Exposure	Deleted the following:  The number and percentage of participants with COVID-19 exposure will be summarized.	Small amount of COVID-19 Exposure data.
5.7.2 Pharmacodynamics	Deleted the following:  Details for PK/PD analyses and potential exposure-response analyses will be described in a separate PK/PD analysis plan.	Not meaningful given the futility decision.
5.7.3 Biomarker Assessments	The exploratory biomarker analyses may be instead of will be performed.	Reduced scope for the abbreviated CSR.
5.7.5 Healthcare Resource Utilization	Deleted	Reduced scope for the abbreviated CSR.
5.7.6.1 Subgroup Analyses for Efficacy	Deleted	Not meaningful given the futility decision.
6.1.5 Prior and Concomitant Medications/Therapies	Added the following listing:  Prophylactic antibiotic medications after receiving meningococcal vaccine for subjects who initiated study drug	Reduced scope for the abbreviated CSR.
6.2.9. Analysis Windows	Added the following:  Table 24. Analysis Windows for Open Label Extension	Incorporating OLE in this SAP.
6.3 Appendix 3. Additional details on Statistical Methods	Deleted	Not needed anymore after analyses updates.
6.4 Appendix 4. Changes to Protocol-planned Analyses	Section renumbered.	Section renumbered.
7. References	Deleted the following reference:  5.Vonesh EF, Greene T, Schluchter MD. Shared parameter models for the joint analysis of longitudinal data and event times. Stat Med. 2006;25(1):143-163. doi:10.1002/sim.2249	Not needed anymore after analyses updates.

